#### 8.4.3 Additional variables

The ratio of the maximum observed concentration ( $C_{\max}$ ) in a dosing interval and the observed concentration at the end of the dosing interval,  $C_{\max}/C_{\min,\tau}$ , which is used to describe levodopa fluctuation during the dosing intervals and other PK variables of levodopa, 3-OMD, carbidopa and ODM-104 will be evaluated as additional variables.

Levodopa fluctuation ratios ( $C_{\max}/C_{\min,\tau}$ ,  $C_{\max}/C_{(16\text{ h})}$ ,  $PTF_{\tau}$  and  $PTF_{(0-16)}$ , and  $AUC_{0-24}$ ,  $C_{\max}$  and  $C_{\min,\tau}$ ) will be the main PK variables of interest.

Drug concentrations will be tabulated by time and treatment with descriptive statistics.

### 8.5 Evaluation and analysis of safety and tolerability

Safety will be evaluated by recording heart rate, systolic and diastolic blood pressure, 12-lead electrocardiogram (ECG), physical examination findings, laboratory safety assessments and

adverse events (AEs). Suicidality will be assessed with the Columbia-Suicide Severity Rating Scale (C-SSRS).

#### **8.5.1 Adverse events**

Adverse events (AEs) reported after administration of the study treatment will be classified by System organ classes (SOC) and preferred terms using the MedDRA dictionary.

The number and proportion (%) of subjects having each AE will be given by treatment group. The numbers will be additionally broken down by severity (mild, moderate, severe) and by the causality (related, not related).

All serious adverse events (SAEs) and other significant AEs will be evaluated case by case. Additionally, narrative descriptions will be included in the study report for all SAEs and certain other significant AEs.

#### **8.5.2 Laboratory safety variables**

Laboratory values and changes from baseline (screening value) in laboratory values will be summarised using descriptive statistics. The number and proportion of subjects with laboratory values outside the normal range will be summarised by visit for each laboratory analyte. Unscheduled laboratory measurements will not be used in tables. They will be included in the listings.

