1.3 Benefit-risk assessment

Healthy subjects in this study will not receive any direct health-related benefit from administration of levodopa, carbidopa and ODM-104. However, the study subjects will receive general information on their current health by laboratory tests, electrocardiograms (ECGs), physical examination including blood pressure (BP) and heart rate (HR) measurements.

Levodopa, carbidopa and ODM-104 have been generally well tolerated and safe in previous PK studies (studies 3112001, 3112002 and 3112003) and in an ongoing study (3112004) in patients with PD; however, they are known to cause different symptoms in some subjects. Headache, nausea, nasopharyngitis, flatulence, vomiting, increased blood creatine phosphokinase, constipation and dizziness were reported relatively frequently in previous PK studies with ODM-104. In addition, isolated cases of cardiac conduction abnormalities and mild increases in liver transaminases were reported. No serious adverse events (SAEs) have been reported in previous phase I studies on ODM-104. Based on these findings as well as the nonclinical data on ODM-104, the events of increase in liver tests, cardiac arrhythmias and gastrointestinal irritation are considered as important potential risks for ODM-104. These risks are subject to close monitoring during the clinical program.

Carbidopa single dose used in the test treatments is higher than those in many levodopa treatments on the market with 4 to 1 levodopa to carbidopa ratio. However, the dosing frequency is 4 times a day and the total daily dose of carbidopa will not exceed the daily dose of the approved levodopa products in this study. Higher carbidopa dose has been used in combination with levodopa and ODM-104 in the previous PK studies and in the ongoing study in patients. In the present study subjects remain in the research institute for the whole duration of the dosing period. Samples for laboratory tests and ECG monitoring are applied to exclude subjects with abnormalities from entering the study and after treatment initiation to be discontinued if specified abnormalities emerge. Signs of nausea, gastrointestinal and other symptoms will be followed clinically daily and if intolerable, treatment will be discontinued.

Blood sampling may cause local pain and haematoma as well as fainting in isolated cases. In addition, ECG electrodes attached to the skin may cause irritation.

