4.5 Removal of subjects from treatment or assessment

Study subjects are free to discontinue the study at any time without providing a reason. However, the investigator should try to identify the reason and document it on the eCRF.

A subject must discontinue the study treatment if the investigator or the sponsor considers the discontinuation to be medically necessary or in the best interest of the subject.

A subject must discontinue the study treatment for example for the following reasons:

- Personal reason
- AE requiring discontinuation of the study treatment, as judged by the investigator:
 - Intolerable dopaminergic AEs such as prolonged moderate or severe vomiting with massive fluid loss and consequent circulatory disorders
 - Intolerable gastrointestinal AEs such as prolonged moderate or severe diarrhoea with massive fluid loss and consequent circulatory disorders
 - Abnormal 12-lead ECG finding of clinical relevance:
 - increase in QTc of >60 ms from baseline
 - increase in QRS of >25% from baseline

- 2nd or 3rd degree atrioventricular block
- sustained (>30 s) cardiac arrhythmias (supraventricular or ventricular tachycardia, atrial fibrillation and/or flutter)
- any symptomatic arrhythmia (except isolated extrasystoles)
- Increase in alanine aminotransferase, aspartate aminotransferase or alkaline phosphatase to >3 x ULN
- Other AE (e.g. fainting or profound weakness) requiring discontinuation of the study treatment
- Lost to follow-up
- Protocol deviation that could affect the outcome of the study, as judged by the investigator
- Other reason (e.g. impossibility to obtain blood samples)

Irrespective of the reason for discontinuation, the subject should be invited to end-of-study assessments as soon as possible. As long as the subject consents, all relevant assessments, at least those of safety, should be performed, preferably according to the schedule for the end-of-study assessments.

The study monitor should be notified about premature discontinuations within 24 h in the event of discontinuation due to an SAE (see section 6.4.1.3) or within 7 days in the event of discontinuation due to another reason.

The sponsor will decide if study subjects who prematurely discontinue will be replaced. Discontinued study subjects are not allowed to re-enter the study.

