6.4.5 Laboratory safety assessments

The following laboratory tests will be taken at the screening visit after at least 10 h of fasting:

Haematology:

- Haemoglobin
- Haematocrit
- Erythrocytes
- Thrombocytes
- Mean corpuscular volume
- Mean corpuscular haemoglobin
- Mean corpuscular haemoglobin concentration
- Leucocytes
- Differential count (lymphocytes, monocytes, eosinophils, neutrophils, basophils)

Clinical chemistry:

- Albumin
- Creatinine
- Alkaline phosphatase
- Alanine aminotransferase

- Aspartate aminotransferase
- Creatine kinase
- Gamma-glutamyl transferase
- Glucose
- Magnesium
- Sodium
- Potassium
- Calcium (albumin corrected)
- C-reactive protein
- Thyroid stimulating hormone
- Total bilirubin

Urinalysis:

- Stick-test: pH, leucocytes¹, nitrites¹, protein, blood¹, glucose (¹ in case of findings, a microscopy examination of urine sediment will be performed)

Serology:

- Human immunodeficiency virus antigen/antibody
- Hepatitis C virus antibodies
- Hepatitis B-surface antigen

Selected laboratory tests

The following selected laboratory tests will be performed on days 1 and 7 in each treatment period, before the first dose:

Haematology:

- Haemoglobin
- Haematocrit
- Erythrocytes
- Thrombocytes
- Mean corpuscular volume
- Mean corpuscular haemoglobin
- Mean corpuscular haemoglobin concentration
- Leucocytes

- Differential count (lymphocytes, monocytes, eosinophils, neutrophils, basophils)

Clinical chemistry:

- Creatine kinase
- Creatinine
- Alkaline phosphatase
- Aspartate aminotransferase
- Gamma-glutamyl transpeptidase
- Alanine aminotransferase
- Total bilirubin
- Sodium
- Potassium
- Magnesium
- C-reactive protein

Urinalysis

- Stick-test: pH, leucocytes¹, nitrites¹, protein, blood¹, glucose (¹in case of findings, a microscopy examination of urine sediment will be performed)

End-of-study laboratory tests

The same laboratory tests as at the screening visit, except determination of thyroid stimulating hormone and albumin, serology tests, urine test for drug abuse and alcohol breath test will be performed.

Alcohol and drug abuse tests during the study

An alcohol breath test will be performed at the screening visit and on admission in each treatment period.

A urine drug abuse test will be performed at the screening visit and on admission in each treatment period.

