The reference ranges of the local laboratories will be recorded on the eCRFs by the sponsor. The investigator's assessment of clinical relevance will be documented on the eCRFs.

In case there are clinically relevant findings, control assessments may be performed according to the judgement of the investigator.

Instructions for the collection, handling, storage and transportation of samples will be provided before the start of the study.

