8.4.5.3 Laboratory safety analysis

Laboratory values and changes from baseline (screening value) in laboratory values will be summarised using descriptive statistics. The number and proportion of subjects with laboratory values outside the normal range will be summarised by visit for each laboratory analyte.

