### 14.3 Safety data

|                |  |
|----------------|--|
| Table 14.3.1.1 | Summary of adverse events during study treatment (subject and event count) |
| Table 14.3.1.2 | Adverse events during study treatment (subject and event count)            |

|                  |   |
|------------------|---|
| Table 14.3.1.3   | Adverse events during study treatment by severity (subject count)                     |
| Table 14.3.1.4   | Adverse events related to study treatment (subject and event count)                   |
| Table 14.3.1.5   | Adverse events during study treatment by severity and causality (event count)         |
| Table 14.3.1.6   | Adverse events before start of study treatment (subject and event count)              |
| Table 14.3.1.7   | Adverse events at the end of study (subject and event count)                          |
| Table 14.3.2.1   | Summary listing of deaths, other serious and significant adverse events               |
| Table 14.3.2.2   | Listing of deaths   |
| Table 14.3.2.3   | Listing of serious adverse events   |
| Table 14.3.2.4   | Listing of adverse events leading to premature discontinuation                        |
| Table 14.3.2.5   | Listing of other significant adverse events   |
| Table 14.3.2.6   | Listing of special situations   |
| Table 14.3.3.1   | Summary listing of narratives of deaths, other serious and significant adverse events |
| Table 14.3.4     | Listing of significant abnormal laboratory values                                     |
| Table 14.3.5.1.1 | Haematology   |
| Table 14.3.5.1.2 | Changes from baseline in haematology  |
| Table 14.3.5.1.3 | Shift tables for haematology variables  |
| Table 14.3.5.2.1 | Chemistry   |
| Table 14.3.5.2.2 | Changes from baseline in chemistry  |
| Table 14.3.5.2.3 | Shift tables for chemistry variables  |
| Table 14.3.5.3   | Serology  |
| Table 14.3.5.4.1 | Urinalysis  |
| Table 14.3.5.4.2 | Shift tables for urinalysis variables - Safety population                             |
| Table 14.3.6.1.1 | Supine heart rate (bpm)   |
| Table 14.3.6.1.2 | Changes from baseline in supine heart rate (bpm)                                      |
| Table 14.3.6.2.1 | Supine diastolic blood pressure (mmHg)  |
| Table 14.3.6.2.2 | Changes from baseline in supine diastolic blood pressure (mmHg)                       |
| Table 14.3.6.3.1 | Supine systolic blood pressure (mmHg)   |

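### SAP 8.5.2 keeps unscheduled laboratory values out of every table, and no worst-value or 3 x ULN summary is listed to pick up a liver-test rise seen only in such a sample

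*SAP*

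**What the plan says.** SAP 8.5.2 plans descriptive statistics for laboratory values and their changes from screening, and out-of-range counts by visit for each analyte. It then adds "Unscheduled laboratory measurements will not be used in tables" and, directly after, "They will be included in the listings". It makes no exception for the abnormality counts. The SAP's list of tables also includes "Shift tables for chemistry variables" (Table 14.3.5.2.3), to which the same rule applies.

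Protocol 8.4.5.3 plans the same counts: "The number and proportion of subjects with laboratory values outside the normal range will be summarised by visit for each laboratory analyte". It does not mention unscheduled samples.

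On sampling, Protocol 6.4.5 says "The following selected laboratory tests will be performed on days 1 and 7 in each treatment period, before the first dose". That panel contains ALT, AST and alkaline phosphatase (ALP). After a clinically relevant finding, "control assessments may be performed according to the judgement of the investigator".

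On the risk, Protocol 1.3 says "the events of increase in liver tests, cardiac arrhythmias and gastrointestinal irritation are considered as important potential risks for ODM-104". Protocol 4.5 includes among its examples of reasons to stop treatment: "Increase in alanine aminotransferase, aspartate aminotransferase or alkaline phosphatase to >3 x ULN".

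**The concern.** Restricting by-visit means and changes to scheduled samples is sound practice, because extra samples come from a selected few subjects at irregular times. Abnormality counts and shift tables serve another purpose: they are meant to show how many subjects had an abnormal value on a treatment, and extra samples are usually taken because something has been noticed. If those samples are barred and no other laboratory table uses them, the treatment-level laboratory summary can understate a risk that the protocol itself names as important. The study compares 0, 50 and 100 mg of ODM-104 to support dose selection for phase III, and each treatment column holds at most about 14 subjects, so one missing case is visible.

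**Working it through.** No figure in the plan needs reproducing. The check sets the sampling schedule against the table rule and the list of outputs.

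**Scheduled chemistry samples per completer** (Protocol Table 3, 6.1.3 and 6.4.5)

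- Screening 1, days 1 and 7 in each of 4 periods, end of study 1: 1 + 4 x 2 + 1 = 10.
- After the first dose of the study: 4 (day 7) + 3 (day 1 of periods 2 to 4) + 1 (end of study) = 8. All 8 are eligible for the tables.

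**Where the schedule has gaps**

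- Nothing is scheduled on days 2 to 6, so any chemistry sample then is unscheduled.
- The day 7 sample follows six days of carbidopa with or without ODM-104, but precedes the first levodopa dose (Protocol 5.3). The next scheduled sample is day 1 of the next period, after a wash-out of at least 4 days (Protocol 1.2.1), or the end-of-study visit, 4 to 21 days after the last dose. Any repeat in between is unscheduled.

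**What the rule does in each case**

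| Case | Laboratory tables | Elsewhere |
|---|---|---|
| Raised in a scheduled sample | Counted | Listings |
| Raised only in an unscheduled sample, normal at the next scheduled one | Not counted | Listings; AE tables if judged an AE |
| Raised on day 7, higher in a control sample | Counted as out of range, but the peak and any crossing of 3 x ULN are not shown | Listings; AE tables if judged an AE |
| Stopped before day 7, sampled at an early end-of-study visit | Depends on how that visit is classed and attributed; the SAP does not say | Listings; AE tables if the stop was for an AE |

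**Is there another laboratory summary that would catch rows 2 and 3?** The SAP's list under 14.3 has values, changes and shift tables for chemistry, and a listing of significant abnormal values (Table 14.3.4). It has no worst-on-treatment table and no count above a multiple of ULN. By contrast, QT and QTcF each have categorical tables (14.3.7.8 and 14.3.7.10).

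**Size per case.** With 14 subjects in a group (Protocol 4.1), one missing subject changes a full treatment column by 1/14 = 7.1 percentage points, for example 0/14 shown where 1/14 occurred. Over all subjects it is 1/56 = 1.8 percentage points. In row 2 the out-of-range count is short by this amount. In row 3 that count is right, and what is missing is the size of the rise. The documents give no rate of unscheduled sampling, so the expected number of cases cannot be calculated.

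**The case against.** The strongest reply is that a case that matters clinically is counted elsewhere. Protocol 4.5 places the 3 x ULN limit under adverse events that require stopping, and Protocol 6.4.1.1 lets an abnormal laboratory finding be an adverse event whatever sample it came from. Such a case enters the adverse event counts by treatment, including the row in Table 14.3.1.1 for events that led to discontinuation. It can also appear in the listings 14.3.2.4, 14.3.2.5 and 14.3.4. This stands, and it limits the concern to the laboratory tables. It does not remove it: a laboratory change becomes an adverse event through a judgement of clinical significance, and the three outputs just named are listings. Neither replaces an objective count against a fixed limit.

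A second reply is that the protocol asks for out-of-range counts by visit, and an unscheduled sample has no visit row. This also stands. A reader might infer that the SAP departs from the protocol, but its sentence can be read as putting the by-visit specification into practice. For that reason the by-visit tables should be left as they are and something added beside them.

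A third reply is that the schedule is not as thin as two samples per period suggests. Day 7 is a post-exposure sample for carbidopa and ODM-104, each period is followed by another scheduled sample, and a rise that persists will be tabulated. This is correct. The gap concerns transient rises and peaks.

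**Conclusion.** The point holds as a limited reporting gap. Read literally, SAP 8.5.2 removes from the laboratory counts and shifts any liver-test rise seen only in an unscheduled sample, and hides the height of a peak seen only there. No listed laboratory summary makes up for it. The size is 7.1 percentage points of a full treatment column per case, at an unknown frequency. This assumes that the sentence means what it says for all tables, and that the output list in the SAP's appendix is complete.

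Two stronger readings are tempting and not supported:

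- **Unscheduled samples are where a rise to the stopping limit is most likely to appear.** The protocol provides control samples after a clinically relevant finding, so the first raised value may well be a scheduled, tabulated one. Nothing in the documents shows that rises would occur mainly on days 2 to 6. A systematic downward bias in the comparison of ODM-104 doses is therefore possible but not shown.
- **A subject stopped within a period contributes only his pre-dose day 1 value.** Protocol 4.5 sends him to end-of-study assessments as soon as possible, and these include ALT, AST and ALP. Whether that sample counts as scheduled, and under which treatment, is left open. That is a gap to close, and it does not establish that the value is lost.

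**What to change.** Amend SAP 8.5.2 and the list of tables as follows.

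1. Keep the by-visit means, changes and out-of-range counts on scheduled samples, as the protocol's by-visit specification implies.
2. Add a summary and a shift table by treatment of each subject's worst value after the first dose of a period and before the first dose of the next, or through end of study for the last period. Use scheduled, unscheduled and early end-of-study samples, and keep screening as baseline.
3. In that summary, add a row counting subjects with ALT, AST or ALP above the protocol's own 3 x ULN limit.
4. State how early end-of-study samples are classed and to which treatment they are attributed. State too that, in the new summary, the pre-dose day 1 sample of periods 2 to 4 belongs to the preceding treatment, because it falls in that treatment's window.
5. Footnote that subjects sampled more often have more chances of an abnormal value.

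The cost is SAP wording and minor programming on data already destined for the listings. No extra sampling is needed and no clinical rule changes. The one drawback is the unequal sampling that the footnote discloses.

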#### **8.5.3 Vitals signs, physical findings, and other observations related to safety**

Vital signs (systolic and diastolic BP and HR) at each visit and change from baseline (screening value) in each vital sign will be summarised using descriptive statistics. 12-lead ECG parameters at each time point and change from baseline (screening value) will be summarised using descriptive statistics. Physical examination and C-SSRS findings will be tabulated.

### **8.6 Additional analyses**

#### **8.7 Changes in the statistical plans from those presented in the clinical study protocol**

#### **8.8 Execution of statistical analyses**

Statistical analyses will be performed by or under the supervision of the Department of Biostatistics and Support Functions of Orion Pharma.

#### **8.9 Software**

Statistical analyses, tables and subject data listings will be performed with SAS® for Windows version 9.4 (SAS Institute Inc., Cary, NC, USA).

## 10 Appendices

### 10.1 List of tables, figures and graphs

#### 14 Post-text tables and figures

##### 14.1 Demographic data

|                |  |
|----------------|--|
| Table 14.1.1   | Disposition of subjects  |
| Table 14.1.2.1 | Reasons for excluding data from the statistical analyses of pharmacokinetic parameters |
| Table 14.1.2.2 | Reasons for study discontinuation  |
| Table 14.1.3   | Demographic and other baseline characteristics   |
| Table 14.1.4   | Medical history and current medical conditions   |
| Table 14.1.5.1 | Prior treatments   |
| Table 14.1.5.2 | Concomitant treatments during study treatment periods                                  |
| Table 14.1.5.3 | Concomitant treatments after end of study treatment                                    |
| Table 14.1.6   | Extent of exposure   |

##### 14.2 Pharmacokinetic data

|                  |   |
|------------------|---|
| Table 14.2.1.1   | Levodopa concentration (ng/ml)  |
| Table 14.2.1.2.1 | AUC tau (h*ng/mL) of levodopa  |
| Table 14.2.1.2.2 | Statistical analysis for AUC tau of levodopa                           |
| Table 14.2.1.3.1 | AUC 0-24 (h*ng/mL) of levodopa   |
| Table 14.2.1.3.2 | Statistical analysis for AUC 0-24 of levodopa                          |
| Table 14.2.1.4.1 | AUC 0-16 (h*ng/mL) of levodopa   |
| Table 14.2.1.4.2 | Statistical analysis for AUC 0-16 of levodopa                          |
| Table 14.2.1.5   | AUC inf (h*ng/mL) of levodopa  |
| Table 14.2.1.6.1 | C max,tau (ng/mL) of levodopa  |
| Table 14.2.1.6.2 | Statistical analysis for C max,tau of levodopa                         |
| Table 14.2.1.7.1 | C max (ng/ml) of levodopa  |
| Table 14.2.1.7.2 | Statistical analysis for C max of levodopa                             |
| Table 14.2.1.8.1 | C min,tau (ng/mL) of levodopa  |
| Table 14.2.1.8.2 | Statistical analysis for C min,tau (ng/mL) of levodopa                 |
| Table 14.2.1.8.3 | Actual C min,tau (ng/mL) of levodopa                                   |
| Table 14.2.1.8.4 | Statistical analysis for actual C min,tau (ng/mL) of levodopa          |
| Table 14.2.1.9.1 | C max / C min ratio tau of levodopa                         |
| Table 14.2.1.9.2 | Statistical analysis of C max / C min ratio tau of levodopa |

|                   |  |
|-------------------|--|
| Table 14.2.1.9.3  | Actual Cmax / Cmin ratio tau of levodopa                         |
| Table 14.2.1.9.4  | Statistical analysis of actual Cmax / Cmin ratio tau of levodopa |
| Table 14.2.1.10.1 | Cmax / C(16h) of levodopa  |
| Table 14.2.1.10.2 | Statistical analysis of Cmax / C(16h) of levodopa                |
| Table 14.2.1.11   | tmax,tau (h) of levodopa   |
| Table 14.2.1.12   | tmax (h) of levodopa   |
| Table 14.2.1.13   | t1/2 (h) of levodopa   |
| Table 14.2.1.14   | Lambda z of levodopa   |
| Table 14.2.1.15.1 | PTFtau of levodopa   |
| Table 14.2.1.15.2 | Statistical analysis for PTFtau of levodopa                      |
| Table 14.2.1.16.1 | PTF0-16 of levodopa  |
| Table 14.2.1.16.2 | Statistical analysis for PTF0-16 of levodopa                     |
| Table 14.2.2.1    | Carbidopa concentrations (ng/ml)                                 |
| Table 14.2.2.2.1  | AUC0-24 (h*ng/mL) of Carbidopa                                   |
| Table 14.2.2.2.2  | Statistical analysis for AUC0-24 (h*ng/mL) of Carbidopa          |
| Table 14.2.2.3.1  | Cmax (ng/ml) of Carbidopa  |
| Table 14.2.2.3.2  | Statistical analysis for Cmax (ng/ml) of Carbidopa               |
| Table 14.2.2.4    | tmax (h) of Carbidopa  |
| Table 14.2.3.1    | 3-ODM concentrations (ng/ml)                                     |
| Table 14.2.3.2.1  | AUC0-24 (h*ng/mL) of 3-ODM                                       |
| Table 14.2.3.2.2  | Statistical analysis for AUC0-24 (h*ng/mL) of 3-ODM              |
| Table 14.2.3.3.1  | Cmax (ng/ml) of 3-ODM  |
| Table 14.2.3.3.2  | Statistical analysis for Cmax (ng/ml) of 3-ODM                   |
| Table 14.2.3.4    | tmax (h) of 3-ODM  |
| Table 14.2.4.1    | ODM-104 concentrations (ng/ml)                                   |
| Table 14.2.4.2    | AUC0tau (h*ng/mL) of ODM-104                                     |
| Table 14.2.4.3    | AUC0-24 (h*ng/mL) of ODM-104                                     |
| Table 14.2.4.4    | Statistical analysis of AUC0-24 (h*ng/mL) of ODM-104             |
| Table 14.2.4.5    | AUCinf (h*ng/mL) of ODM-104                                      |
| Table 14.2.4.6    | Cmax,tau (ng/ml) of ODM-104                                      |
| Table 14.2.4.7    | Cmax (ng/ml) of ODM-104  |
| Table 14.2.4.8    | Statistical analysis of Cmax (ng/ml) of ODM-104                  |
| Table 14.2.4.9    | Cmin,tau (ng/ml) of ODM-104                                      |
| Table 14.2.4.10   | tmax,tau (h) of ODM-104  |
| Table 14.2.4.11   | tmax (h) of ODM-104  |
| Table 14.2.4.12   | t½ (h) of ODM-104  |
| Table 14.2.4.13   | Lambda z of ODM-104  |

